12.5.2 Safety endpoints

For all safety analyses, the safety set will be used and will be presented by actual investigational treatment as participant first received after randomization.

Safety summaries (tables, figures) include only data from the on-treatment period with the exception of baseline data which will also be summarized where appropriate (e.g. change from baseline summaries). The on-treatment period lasts from the date of first administration of study treatment to 30 days after the date of the last actual administration of any study treatment.

A separate summary for death including on treatment and post treatment deaths will be provided.

12.5.2.1 Adverse Events

The number (and percentage) of participants with treatment emergent adverse events (events started after the first dose of study medication or events present prior to start of double-blind treatment but increased in severity based on preferred term) will be summarized in the following ways:

- by treatment, primary system organ class and preferred term.
- by treatment, primary system organ class, preferred term and maximum severity.
- by treatment, Standardized MedDRA Query (SMQ) and preferred term.

A participant with multiple adverse events within a primary system organ class is only counted once towards the total of the primary system organ class.

Separate summaries will be provided for study medication related adverse events, serious adverse events, other significant adverse events and adverse events leading to study drug discontinuation.

Participants who died any time during the study will be listed with SAEs leading to such deaths.

12.5.2.2 Clinical laboratory evaluation

Summary statistics for standard laboratory test results will be provided by treatment and visit/time. Shift tables using the low/normal/high/ (low and high) classification will be used to compare baseline to the worst on-treatment value.

Number (percent) of participants with post-treatment changes in lab parameters related to hepatotoxicity (ALP, ALT, AST, or bilirubin elevations as outlined in Section 10.2.1 and Table 16-2) will also be summarized.

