- 23. Symptomatic genital or urinary tract infection within 4 weeks prior to randomization or participants with high risk as, determined by the investigator (including concomitant therapy with immunosuppressive potential), to be particularly susceptible to genital or urinary tract infection.
- 24. Recent history of gastrointestinal disorder associated with chronic diarrhea.
- 25. Any history of and/or suspected Fournier's gangrene, or participants with high risk as, determined by the investigator (including concomitant therapy with immunosuppressive potential), to be particularly susceptible to Fournier's gangrene.
- 26. Diabetic foot ulcer within 4 weeks prior to randomization.
- 27. History of inflammatory bowel disease (ulcerative colitis, Crohn's disease).
- 28. Known positivity for Human Immunodeficiency Virus (HIV) infection. HIV antigen/antibody tests will be performed to determine HIV status if allowed and required according to local regulations.
- 29. History of malignancy of any organ system (other than localized basal cell carcinoma of the skin or in situ cervical cancer), treated or untreated, within the past 5 years, regardless of whether there is evidence of local recurrence or metastases.
- 30. History or evidence of ongoing drug abuse, within the last 6 months prior to randomization.
- 31. Use of other investigational drugs within 5 half-lives of randomization, or within 30 days, whichever is longer.

- 32. Previous exposure to any other investigational or recently (2019 onwards) approved NASH treatment within 6 months prior to qualifying biopsy (participants known to have only received placebo may be included).
- 33. Sexually active males must use a condom during intercourse while taking drug and for 5 days after stopping investigational medication and should not father a child in this period. A condom is required to be used also by vasectomized men in order to prevent delivery of study drug via seminal fluid. (With-amendment version 01, this exclusion criterion is no longer applicable).
- 34. Women of child-bearing potential, defined as all women physiologically capable of becoming pregnant, unless they are using highly effective methods of contraception during dosing and for 5 days (> 5 times the terminal half-life) after stopping of investigational medication. Highly effective contraception methods include:

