¹¹ Women Of Child Bearing potential (WOCBP) must have a urine dipstick pregnancy test every 4 weeks, including at week 28, 36 and 44 (when there are no study visits), up to and including the follow up visit.

¹² After Baseline visit onwards serum sample to be collected for serum pregnancy test only if urine dipstick test is positive – During the study if test is positive, the participant must be discontinued from study drug.

¹⁷ At Baseline and week 4, to be collected at least 1-2 hours post dose at clinic.

¹⁸ Update as necessary

¹⁹ Update as necessary - SAEs must be reported & recorded until 30 days after the participant has stopped study participation; see appropriate protocol Section 10.1.2.

²¹ For participants who discontinue study treatment prematurely before the end of the treatment period for any reason other than withdrawal of informed consent, the Week 48, End of Treatment (EOT) and Week 52 End of Study (EOS) visits must be performed.

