**Analysis visit** is the visit label derived based on study day of assessment and the analysis visit windows defined in Table 2-1. For laboratory and bioanalytical parameters specified for both Group 1 and Group 2 in Table 2-1, two sets of analysis visits will be derived and will be referred to as "**AV1**" and "**AV2**" respectively. The AV1 is derived according to Group 1 for by visit analysis on full analysis set (FAS). For AV2, assessments >14 days after the last dose date will be slotted into the analysis visit window for follow up visit for by-visit analysis of laboratory data on safety analysis set (SAF).

**Analysis visit windows** are non-overlapping periods each associated with a visit planned in protocol and all together cover the entire study period of a patient. If multiple measurements of same parameter for a patient fall in the same window, the value of this analysis visit is selected according to Table 2-2. If no assessment falls into a window, the value of that analysis visit will be set to missing unless imputation rule(s) are defined for the parameter. Repeat and unscheduled visits will be mapped to analysis visits in the same way as scheduled visits.

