#### 2.8.3 Laboratory data

Summary statistics of values and changes from baseline will be provided by visit (AV2) and by study treatment for laboratory tests listed in Table 2-6. Change from baseline will be summarized for patients with both baseline and post baseline values.

laboratory test group	Parameters	
Hematology	Hemoglobin (Hb), Hematocrit (Hct), Red blood cells (RBC), Mean corpuscular volume (MCV), Platelets, White blood cells (WBC), absolute WBC differential counts ((Neutrophils, Lymphocytes, Monocytes, Eosinophils, Basophils separately)	
General Clinical Chemistry	Sodium, potassium, chloride, bicarbonate, calcium, magnesium, phosphorus, uric acid, haptoglobin	
Liver	ALT, AST, ALP, GGT, creatine kinase (CK), lactate dehydrogenase (LDH), total bilirubin, albumin, total protein	
Renal	BUN, creatinine, estimated glomerular filtration rate (eGFR)	
Urinalysis	Albumin-creatinine ratio (ACR), Protein-creatinine ratio (PCR)	
Coagulation	INR, APTT, Prothrombin Time (PT) and Thrombin Time (TT)	
Lipids and vascular risk	Total cholesterol, HDL-C, LDL-C, VLDL-C, triglycerides, free glycerol and free fatty acids, ApoAI, high sensitivity C-reactive protein (hsCRP)	

 Table 2-6
 Laboratory safety endpoints

Shift tables for normal / abnormal (low and high based on the low/normal/high classifications from central lab) from baseline to the most extreme post-baseline value will be provided.

Number (%) of patients with post-treatment changes in laboratory criteria related to hepatotoxicity or nephrotoxicity criteria (Section 5.3.1) will also be summarized by criteria and by study treatment. In addition, patients meeting a criterion for hepatotoxicity, nephrotoxicity or other notable abnormalities defined in Section 5.3.1 will be listed, including the criteria met as well as the laboratory test name, date (study day) of lab sampling, results and units for that test and related lab tests throughout the study.

Novartis	For business use only	Page 28
SAP		CLJN452D12201C

For summaries of shift, hepatotoxicity/nephrotoxicity events or other notable laboratory abnormalities outlined above, all post-treatment data will be used regardless of last dose date.

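### SAP 2.8.3 counts laboratory values at any time after the last dose in shift and toxicity summaries, whereas the protocol stops at last dose + 30 days

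*Protocol*

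**What the plan says.** **Protocol.** Section 12.5.2 sets a general rule: "Safety summaries (tables, figures) include only data from the on-treatment period". It excepts baseline data and adds a separate summary of deaths. The period runs from first dose "to 30 days after the date of the last actual administration of any study treatment". Section 12.5.2.2 then says of the low/normal/high grouping in the shift tables that this "classification will be used to compare baseline to the worst on-treatment value". Its next sentence plans a hepatotoxicity summary in looser terms: "Number (percent) of participants with post-treatment changes in lab parameters related to hepatotoxicity". The section plans no nephrotoxicity table.

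**SAP.** Section 2.8 repeats the 30-day default but allows exceptions where they are stated. Section 2.8.3 states one. The shift tables use the most extreme value after baseline, and for shift, hepatotoxicity, nephrotoxicity and other notable laboratory abnormalities, "all post-treatment data will be used regardless of last dose date". Section 4 lists the significant changes from the protocol, and no visible item there covers the laboratory data window.

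**Late values.** Footnote 21 of protocol Table 8-1 says that for participants who stop treatment prematurely, unless they withdraw consent, "the Week 48, End of Treatment (EOT) and Week 52 End of Study (EOS) visits must be performed". Laboratory tests are scheduled at both visits.

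**The concern.** The two documents give different answers to a simple programming question: is an ALT value drawn five months after the last dose part of the shift or toxicity count for that arm? Under the protocol it is not; under the SAP it is. Because the most extreme value decides each participant's category, one late result is enough to change it.

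Time at risk of being counted also differs. Under the protocol rule it ends 30 days after the last dose. Under the SAP rule it runs as long as the participant keeps attending. If early stopping differs between arms, the SAP tables mix on-drug and off-drug experience in different proportions by arm, under the label of the treatment received. A reader who relied on the protocol's definition would misread the tables.

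**Working it through.** There is no sample size, power or alpha figure to reproduce. The check compares the two texts and then does day arithmetic.

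**1. Rule by table type**

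| Summary | Protocol | SAP 2.8.3 | Conflict |
|---|---|---|---|
| Shift tables | Worst on-treatment value (12.5.2.2), ending at last dose + 30 days (12.5.2) | Most extreme value after baseline, no cut-off | Direct |
| Hepatotoxicity | Loose wording in 12.5.2.2; general 30-day rule in 12.5.2 | No cut-off | Through the general rule only |
| Nephrotoxicity, other notable values | No specific plan in 12.5.2.2; general 30-day rule in 12.5.2 | No cut-off | Through the general rule only |

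**2. Who is affected**

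Inputs are the visit days in protocol Table 8-1 (baseline Day 0, Week 48 = Day 336, Week 52 = Day 364) and the 30-day limit in 12.5.2. Let L be the day of last dose. A visit on day D is counted by the SAP but not by the protocol when D − L > 30, that is, when L < D − 30.

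- Week 48: L < 336 − 30 = 306.
- Week 52: L < 364 − 30 = 334.
- Completer with last dose on Day 336: 364 − 336 = 28 days at Week 52. Both rules count the value.

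The SAP numbers the first dose as Day 1, so in its numbering the limits are Days 307 and 335. The gaps in days are unchanged.

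**3. How late the extra values can be**

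This assumes that the participant attends every remaining visit on its scheduled day.

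| Last dose | Visits counted only by the SAP | Days off drug |
|---|---|---|
| Day 28 | Weeks 12 to 52 | 56 to 336 |
| Day 84 | Weeks 20 to 52 | 56 to 280 |
| Day 168 | Weeks 32, 40, 48, 52 | 56, 112, 168, 196 |
| Day 280 | Weeks 48, 52 | 56, 84 |
| Day 336 | None | Not applicable |

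**4. Whether such values will exist**

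The protocol is not of one mind. Footnote 21 of Table 8-1 requires Week 48 and Week 52 visits after an early stop. Section 9.3 places the safety follow-up visit 4 weeks after last treatment, for early discontinuers as well. That is 28 days, inside the 30-day limit, so a value from that visit is treated alike by both rules. Section 8 asks for the end-of-treatment visit as soon as possible after stopping. Section 9.1.1 sets a minimum of concomitant treatments and adverse events, by telephone if necessary, with no laboratory tests. The volume of late values therefore depends on which text the sites follow.

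**The case against.** **Late liver values can matter.** Counting everything after baseline may catch delayed injury, so inclusion is not wrong in itself. This stands, and it is a reason to display late values separately and not to discard them. It does not remove the contradiction. The protocol's remark about contraception "for 5 days (> 5 times the terminal half-life) after stopping of investigational medication" does not settle the matter either way, since it says nothing about delayed hepatotoxicity.

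**The exception is stated and the values are traceable.** SAP 2.8 allows exceptions. SAP 2.8.3 lists every participant who meets a hepatotoxicity, nephrotoxicity or notable-value criterion, with study days, and SAP 2.1 puts first and last dose dates on all listings. No safety hypothesis test is planned. This stands for the toxicity criteria. It does not help the shift tables, where the contradiction is direct, because a low/normal/high shift alone does not trigger that listing.

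**The SAP is old.** It is dated 09-Dec-2019, describes the three-arm design with 210 patients and expects to be amended. Its section 4 was written against the protocol then in force, and item 4.10 is blank in this copy, so an entry there cannot be ruled out. That is why the point is limited to visible items. The rationale in the Amendment 01 log mentions summaries of off-treatment data, but the current 12.5.2 and 12.5.2.2 still restrict them.

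**Stronger readings that the documents do not support.**

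- *Three competing windows.* The SAP 2.1.1 rule that "assessments >14 days after the last dose date will be slotted into the analysis visit window for follow up visit" assigns a visit label in by-visit tables. It excludes nothing and does not govern shift or toxicity counts.
- *A head count.* A reader might take the SAP's 10% dropout or the protocol's 20% missing Week 48 biopsies and obtain 380 × 0.10 = 38 to 380 × 0.20 = 76 participants. Those who leave the study give no late samples, and a missing biopsy does not show late attendance. The relevant group stops drug and keeps attending, and no rate is given for it.
- *Inflated hepatotoxicity on active drug.* The protocol reports lower transaminases on both drugs, entry allows ALT/AST up to 5 × ULN, and SAP 5.3.1 uses absolute limits such as 3 × ULN. A return to a high untreated level could therefore be flagged. But such a participant may already be flagged at Weeks 2, 4 or 8 under either rule, and background abnormalities can arise off drug in any arm.

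**Conclusion.** Wrong as written: the SAP's laboratory rule contradicts the protocol's. This is certain for shift tables, where both documents name the value to be used. For hepatotoxicity, nephrotoxicity and notable values it rests on reading the general rule in protocol 12.5.2 as covering them; the loose hepatotoxicity wording in 12.5.2.2 states no exemption from it.

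The reach is limited to participants who stop early and continue to give samples, with last dose before Day 306 for the Week 48 value and before Day 334 for the Week 52 value, given visits on their scheduled days. Completers are untouched. How many participants this concerns, and which arm it would favour, cannot be derived from the documents. The case for correction rests on the inconsistency and the ease of repair, not on a demonstrated bias.

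**What to change.** 1. In SAP 2.8.3, change the last sentence and the shift-table wording so that the main shift, hepatotoxicity, nephrotoxicity and notable-value tables use first dose through last dose + 30 days, in line with protocol 12.5.2 and 12.5.2.2.
2. Show later values in the same tables in a separately labelled off-treatment row, so that delayed abnormalities stay visible.
3. If the sponsor intends any departure from the protocol window, record it with its reason in SAP section 4.
4. When the SAP is updated to the four-arm design, have footnote 21 of Table 8-1 and section 9.3 of the protocol reconciled on the timing of visits after an early stop, since that decides how many late values there will be.

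The cost of the table change is a small edit to SAP 2.8.3 and one extra row per table. No new data are needed.

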12.5.2.3 Vital signs

The change from baseline in vital sign parameters, including Anthropometric measurements, will be summarized at scheduled post-baseline visits by treatment group. Change from baseline will only be summarized for participants with both baseline and post-baseline values.

[figure not shown]
Participants with clinically notable vital signs as defined in Section 16.1 will be listed.

12.5.2.4 ECG

PR, QRS, QT, QTcF, and RR intervals will be obtained from 12-lead ECGs for each participant during the study. ECG data will be read and interpreted centrally.

Number of participants changing in normal or abnormal ECG will be summarized by treatment and scheduled visit.

The Fridericia QT correction formula (QTcF) will be used for clinical decisions and for analyses. Notable QTcF values and changes from baseline will be summarized by treatment and scheduled visit, where a notable value is defined as a QTcF \geq 450 msec (male) or \geq 460 msec (female) and the categories used for the change (increase) in QTcF are: \leq 30 ms, > 30 to \leq 60 ms and > 60 ms.

12.7 Interim analyses

No interim analysis is planned for the study. Analysis needed for safety review by DMC will be defined in a separate DMC charter.

12.8 Sample size calculation

Sample size and allocation are determined by three factors:

- 1. Optimizing the power of passing at least one of the combination vs. placebo tests from the two primary endpoints;
- 2. Optimizing the power of passing any monotherapy vs placebo test (given that at least one of the combination vs. placebo tests have succeeded);
- 3. Restricting the size of placebo arm no larger than that of any treatment arm.

12.8.1 Primary endpoint(s)

Assumptions about true histological response rates for various treatments and placebo are made for sample size calculation. Published studies so far (Table 12-2) suggest unignorable placebo effect ranging from 8% to 18% for different populations and endpoints, but unpublished studies indicate some even higher placebo rates. For each primary endpoint, the response rates of the two monotherapies are assumed to be similar to each other and higher than that of placebo, and the response rate of the combination therapy is deemed to be the highest.

Novartis Amended Protocol Version 02 (Clean) Confidential

Table 12-2	Placebo effects on histological responses

Table 12-2 Placebo effects of histological responses					
Histological Response definition	Time point	Histological study	NASH population with Fibrosis stages	Placebo response rate	
Fibrosis	Month 18	REGENERATE	F1 + F2 + F3	10.6%	
improvement of 1 stage and no		(2019) Obeticholic acid	F2 + F3	11.9%	
worsening in NASH	Week 52	CENTAUR (2018)	F1 + F2 + F3	10.4%	
		Cenicriviroc			
	Week 52	ARREST (2018)	F1 + F2 + F3	17.5%	
		Aramchol			
	Week 48	STELLAR3 (2019)	F3	13.2%	
		Selonsertib			
	Week 48	STELLAR4 (2019) Selonsertib	F4	12.8%	
NASH resolution with no worsening in Fibrosis	Month 18	REGENERATE (2019)	F1 + F2 + F3	8%	
		Obeticholic acid	F2 + F3	7.9%	
	Week 52	GOLDEN (2016) Elafibranor	F0+F1+F2+F3	9%	

Table 12-3	Response rate setting used for sample size and power calculation	

Treatment	True Response Rate			
Primary Endpoint	Combination	LJN452	LIK066	Placebo
At least one stage improvement in fibrosis without worsening of NASH	35%	30%	30%	20%
NASH resolution without worsening of fibrosis	25%	20%	20%	10%

Table 12-3 shows the assumed response rates of treatments and placebo under the two primary endpoints. Since both endpoints involve fibrosis and NASH, it is reasonable to expect these endpoints associated with each other. The participant level correlation of the two endpoints is set at +0.5 to be conservative in evaluating sample size and power.

Sample size is first determined by reaching 80% power for passing the combination therapy vs. placebo test on at least one of the primary endpoints under equal allocations of the four arms. Table 12-4 displays the powers under various sample sizes. From the table, it is clear to see that a sample size of 380 can obtain 80% power for the tests of interest.

Confidential

Amended Protocol Version 02 (Clean)

 Table 12-4
 Powers of different sample sizes upper sizes upper

able 12-4 Powers of different sample sizes under equal allocation	
---	--

Sample Size					Power		
Total	LJN452	LIK066	Combo	Placebo	Cmb vs. Plc on Endpoint A	Cmb vs. Plc on Endpoint B	Cmb vs. Plc on at least one of Endpoint A and B
200	50	50	50	50	0.31	0.42	0.52
220	55	55	55	55	0.33	0.45	0.56
240	60	60	60	60	0.37	0.49	0.60
260	65	65	65	65	0.39	0.53	0.63
280	70	70	70	70	0.41	0.57	0.67
300	75	75	75	75	0.45	0.60	0.70
320	80	80	80	80	0.47	0.62	0.72
340	85	85	85	85	0.50	0.65	0.75
360	90	90	90	90	0.51	0.68	0.77
380	95	95	95	95	0.55	0.72	0.80
400	100	100	100	100	0.57	0.73	0.82

After total sample size is fixed, allocation of the four arms is assessed based on three factors:

- 1. Increasing the power of passing at least one of the combination vs. placebo tests from the two primary endpoints;
- 2. Slightly decreasing the power of passing any monotherapy vs placebo test (given that at least one of the combination vs. placebo tests have succeeded);
- 3. Constraining the size of placebo arm no larger than that of any treatment arm.

Table 12-5	Powers of passing at least one of the combination vs. placebo tests
	under various allocations of 380 participants

Sample Size				Power	
LJN452	LIK066	Combo	Placebo	Cmb vs. Plc on at least one of Endpoint A and B	
34	34	278	34	0.72	
49	49	233	49	0.80	
65	65	185	65	0.84	
80	80	140	80	0.85	
95	95	95	95	0.80	
110	110	50	110	0.62	

According to Table 12-5, allocation of 80 (LJN452), 80 (LIK066), 140 (Combo), and 80 (placebo) provides good power for passing at least one of the combination therapy vs. placebo tests from the two primary endpoints.

Power calculations were performed with simulations (n=100000) implemented in R 3.5.3, where the primary analysis in each simulated study was performed using z-tests of difference in proportions without continuity correction for simplicity.

Novartis	Confidential	Page 146 of 160
Amended Protocol Version 02 (Clean)		Protocol No. CLJN452D12201C
The missing Week 48 biopsy rate of the	e study is anticipated to	be around 20%. The missing
response data due to intercurrent event	s will be addressed wit	h intercurrent event strategies

specified in ICH E9, whereas those not related to intercurrent events will be substituted with certain multiple imputation methods. Sample size adjustment is not needed because the treatment response rates are already assumed with conservative values.

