Combination vs. placebo (test 1, k = 1, i = Cmb, j = Plc)

Tropifexor (LJN452) vs. placebo (test 2, k = 2, i = LJN, j = Plc); licogliflozin (LIK066) vs. placebo (test3, k = 3, i = LIK, j = Plc)

Combination vs. tropifexor (LJN452) (test 4, k = 4, i = Cmb, j = LJN); combination vs. licogliflozin (LIK066) (test 5, k = 5, i = Cmb, j = LIK)

There are ten potential tests to be performed for the two primary endpoints (five for each primary endpoint), and it is important to control the overall Type I error rate for these tests. The alpha recycling graph presented in Figure 12-1 shows how alpha transfers among them. If the data fails to reject the null hypothesis of a test, then the alpha of that test will not be passed to others. This restriction ensures the control of overall Type I error rate. Again, for the primary

Confidential

Amended Protocol Version 02 (Clean) Protocol No. CLJN452D12201C endpoints, the overall alpha is set at two-sided 5%. A logistic regression model with the logit of probability for histological response as the dependent variable, treatment groups as the main effect, baseline fibrosis stage and T2DM (No/Yes) as explanatory variables, and the baseline BMI as a covariate will be utilized to test the hypotheses at each step. While this model will be the typical logistic regression in most cases, it should be set as the Firth logistic regression if some arm (such as the placebo) has a low response rate, as the Firth method returns less biased results for data with rare events. The null hypothesis of *k*th test, if executed, will be rejected if the p-value for the coefficient of treatment effect in the *k*th comparison is less than or equals to its corresponding alpha. If no alpha is passed to a specific comparison, then its corresponding test will not be performed and p-value will not be calculated. More statistical specifications of the model will be described in the statistical analysis plan (SAP).

The number and percentages of histological responders at week 48 in FAS will be summarized by treatment groups. The difference between the treatment of interest and the alternative treatment will be presented along with 95% confidence interval calculated based on the normal approximation for distribution of the difference between two binomial random variables.

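### The power figures in Protocol Tables 12-4 and 12-5 come from an unpooled z-test on complete data; the planned logistic test gives less power and little gain from 1.75:1:1:1

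*Protocol*

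**What the plan says.** Protocol 12.8.1 sizes the trial on the chance that the combination beats placebo on at least one of the two primary endpoints. Table 12-3 assumes 35% vs 20% for the fibrosis endpoint (A) and 25% vs 10% for NASH resolution (B), with a correlation of 0.5 between them. From Table 12-4 it concludes that "a sample size of 380 can obtain 80% power for the tests of interest", at equal allocation. Table 12-5 then shows 0.85 at 140 combination and 80 placebo against 0.80 at 95 and 95, and 1.75:1:1:1 is adopted. The simulation method is disclosed: "the primary analysis in each simulated study was performed using z-tests of difference in proportions without continuity correction for simplicity".

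The planned test is in Protocol 12.4.2. It is a logistic regression with treatment, baseline fibrosis stage, T2DM and BMI, and each null hypothesis "will be rejected if the p-value for the coefficient of treatment effect in the" relevant comparison falls at or below its alpha. The model changes in one case: "it should be set as the Firth logistic regression if some arm (such as the placebo) has a low response rate".

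On missing data, 12.8.1 expects about 20% of Week 48 biopsies to be missing. Intercurrent-event cases follow the estimand strategies, and "those not related to intercurrent events will be substituted with certain multiple imputation methods". It concludes: "Sample size adjustment is not needed because the treatment response rates are already assumed with conservative values".

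**The concern.** The tabulated power belongs to one test and the trial will be decided by another. The words "for simplicity" would be harmless if the two agreed closely at every allocation. They do not: the z-test that reproduces the tables is liberal at the unequal allocation it was used to support. The 0.85, and the 5-point advantage over equal allocation, are therefore not properties of the planned analysis.

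The missing biopsies are a second gap. Protocol 12.4.3 counts a participant with no Week 48 biopsy as a non-responder. Section 12.4.4 uses early-termination histology after at least 24 weeks of treatment, and otherwise multiple imputation. No split between these routes is given, and nothing says whether the Table 12-3 rates are already net of non-response. A reader who meets a negative result in this Phase 3 enabling study would judge it against a power that the plan has not shown.

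**Working it through.** **Inputs.** Table 12-3 rates and correlation 0.5 (12.8.1). Overall two-sided 5% split evenly, so two-sided 0.025 per endpoint and critical value 2.241; success is a win on A or B (12.4.2). Arm sizes from Tables 12-4 and 12-5.

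**Step 1: reproduce the tables.** Correlated binary pairs were simulated, 400,000 trials per row, counting a favourable rejection on A or B.

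| Combination:placebo | Stated | Unpooled z | Pooled z | Likelihood ratio | Wald | Firth-Wald |
|---|---|---|---|---|---|---|
| 278:34 | 0.72 | 0.715 | 0.480 | 0.578 | 0.372 | 0.301 |
| 233:49 | 0.80 | 0.797 | 0.660 | 0.710 | 0.612 | 0.558 |
| 185:65 | 0.84 | 0.840 | 0.754 | 0.793 | 0.737 | 0.707 |
| 140:80 | 0.85 | 0.850 | 0.801 | 0.818 | 0.780 | 0.763 |
| 95:95 | 0.80 | 0.801 | 0.788 | 0.793 | 0.773 | 0.759 |
| 50:110 | 0.62 | 0.607 | 0.694 | 0.665 | 0.672 | 0.669 |

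Only the unpooled z-test at full N follows the stated column. The last three columns are logistic tests without covariates. The four-arm model with the three covariates included but given no effect (30,000 trials) agrees. Likelihood ratio, Wald and Firth are 0.815, 0.781 and 0.759 at 140:80, and 0.796, 0.778 and 0.762 at 95:95.

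**Step 2: why the allocation gain shrinks.** Take endpoint B.

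- Unpooled z is 0.15/√(0.1875/n₁ + 0.09/n₀). At 95:95 this is 0.15/0.05405 = 2.775; at 140:80 it is 0.15/0.04964 = 3.022.
- Wald z is ln 3/√(1/(0.1875 n₁) + 1/(0.09 n₀)), with ln 3 = 1.0986. At 95:95 this is 1.0986/0.4160 = 2.641; at 140:80 it is 1.0986/0.4207 = 2.611.

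On the difference scale the combination arm has the larger variance, so moving participants into it helps. On the log-odds scale the placebo arm has the larger variance, so taking participants out of it costs about as much as is gained. Across both endpoints and the two sets of simulations, the gain of 140:80 over 95:95 is 4.9 points (unpooled z), about 2–2.5 (likelihood ratio), 0.3–0.8 (Wald) and −0.3 to +0.4 (Firth).

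**Step 3: behaviour under no effect (20%/10% in both arms).** Favourable rejection on either endpoint should be at most 2.5%. At 140:80 it is 3.6% for unpooled z, 2.5% likelihood ratio, 1.4% Wald and 1.1% Firth. At 95:95 it is 2.5%, 2.4%, 1.9% and 1.6%. The unpooled test is liberal at 140:80 and not at 95:95.

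**Step 4: covariates.** The documents give no effect sizes, so these are assumptions with the marginal rates held. Moderate effects (for example odds ratios of 1.5 to 2 for fibrosis stage and T2DM, and 1.5 per SD of BMI) give about 0.77–0.85 at 140:80 across the three logistic tests. Strong effects (3, 3 and 2) give 0.84–0.88. The allocation gain stays at about 0–2.5 points.

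**Step 5: 20% missing at 140:80, equal across arms, if Table 12-3 excludes non-response.**

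- All non-responders: rates × 0.8, so 28%/20% vs 16%/8%. Wald 0.63–0.64, Firth 0.60.
- Complete cases, as a proxy for imputation: 112:64. Wald 0.67, Firth 0.64.
- 10 points non-response, 5 early-termination histology, 5 imputed: 0.68 / 0.65 (Wald / Firth).
- 5 points non-response, 15 early-termination histology: 0.74 / 0.73.

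If Table 12-3 is already net of non-response, there is no further loss from that route.

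**Step 6: what the claimed conservatism is worth.** At the published F2+F3 placebo rates in Table 12-2 (11.9%/7.9%), with all missing as non-responders, power is about 0.90 (Firth) to 0.92 (Wald) if the combination stays at 35%/25%. If instead the 15-point difference is held (26.9%/22.9%), it is about 0.67–0.70.

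**The case against.** The strongest reply is that nothing is hidden and nothing is miscalculated. The z-test is named, the missing rate is stated, and a reason is given for not adjusting. That stands: a reader might infer that Tables 12-4 and 12-5 contain an arithmetic error, and they do not.

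Second, the covariates are in the model because they are expected to matter. SAP 5.4.1, although written for the superseded three-arm design, expects BMI and T2DM to be prognostic. The no-effect case is therefore a lower end, and only strong assumed effects bring Wald or Firth power to about 0.85. The choice of Wald is also an inference. Protocol 12.4.2 does not name the p-value type; pooling by Rubin's rules in 12.4.4 points to Wald, as does the MIANALYZE step in SAP 5.4.2. The likelihood ratio figure belongs in the range for that reason. Firth depends on a low response rate that is not defined.

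Third, the assumed rates may well be conservative: every published placebo rate in Table 12-2 is below the 20%/10% assumed. But 12.8.1 also says that "unpublished studies indicate some even higher placebo rates", and Step 6 shows that the claim turns on what is assumed for the combination.

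A reader might also infer that the monotherapy cost of 140:80, described as "Slightly decreasing the power of passing any monotherapy vs placebo test", is larger under the planned test. The documents do not support that. The answer depends on alpha weights that are not in the readable text. It also depends on whether that factor is a joint probability or one conditional on a combination win; on the conditional reading the cost is nearly the same for every test.

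**Conclusion.** The point holds as one about the stated power and its justification. With the planned test, complete data and no covariate effect, power at 140:80 is about 0.76–0.78 (Firth/Wald) or 0.82 (likelihood ratio), not 0.85. At 95:95 it is about 0.76–0.79, not 0.80. The gain from unequal allocation is about 0–2.5 points, not 5. These figures rest on the Table 12-3 rates and correlation 0.5.

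The missing-biopsy loss is conditional. It runs from none, if Table 12-3 already counts non-response or all missing cases have usable early-termination histology, down to about 0.60–0.64 (Firth/Wald) if it does not and all are non-responders. A reader might infer that true power is 0.60, that the trial needs more participants, or that 1.75:1:1:1 was the wrong choice. None of these follows: the split of missing cases is not given, the assumed rates may be conservative, and 140:80 is still best or level among the rows listed.

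**What to change.** Re-run Tables 12-4 and 12-5 with the planned logistic/Firth test. Name the p-value type (Wald through Rubin's rules, or likelihood ratio) and the covariate effects assumed, and restate the power and the allocation gain from that run. Add one row with 20% missing biopsies and its assumed split between non-response, early-termination histology and multiple imputation. Replace the sentence that no adjustment is needed with a statement of whether Table 12-3 already counts missing biopsies as non-response. If power at published placebo rates is offered as evidence of conservatism, state the combination rate that goes with it.

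The cost is a repeat of an existing simulation with a different test and one missing-data step, plus a reworded sentence. The stated power may become less favourable. Enrolment, allocation and conduct do not change.
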